9.7.3 Analysis of Effectiveness

- ① Mean, standard deviation, minimum value, maximum value, and median of changes in glycosylated hemoglobin(HbA1c) and fasting plasma glucose(FPG), weight, and blood pressure, which were measured at the last visit versus baseline, should be presented, and if there is a difference before administration versus after administration should be analyzed using paired t-test.
- ② If there is difference in the change of glycosylated hemoglobin (HbA1c) according to demographic parameters mentioned in 9.7.1 should be analyzed using t-test or ANOVA (Analysis of Variance).
- ③ The frequency and percentage of patients who had glycosylated hemoglobin(HbA1c) reaching less than 7% (target effectiveness response rate) at the last visit should be calculated, and the frequency and percentage of patients with glycosylated hemoglobin(HbA1c) decreased by at least 0.5% at the last visit should be calculated.
- ④ For final effectiveness evaluation (improved, unchanged, aggravated, unassessable) and 'effective(improved)'/‘ineffective(unchanged, aggravated)’, the number and

percentage of subjects should be mentioned. The final effectiveness evaluation of “Improved” will be classified as “Effective”, “Unchanged” and “Aggravated” will be classified as “Ineffective”. The effectiveness rate and its 95% confidence intervals will be estimated with exact method.

- ⑤ To estimate any factors that are thought to influence an effective ratio, logistic regression analysis should be conducted, and for statistically significant parameters, the meaning should be described.

9.7.4 **Interim Analyses**

In accordance with local regulation for NIS, interim analyses are planned biannually for the initial two years and annually thereafter.

9.7.5 **Handling of Missing Data**

Maximum attempt will be made to ensure the completeness of data collection. All available data will be used in the data analysis.

9.8 **QUALITY CONTROL**

All entries in the eCRF and the existing codings will be stored in a database. The structure of the database is based on the division into sections and entry fields defined in the eCRF. To improve and ensure data quality, data checks will be performed automatically in the eCRF directly on electronic entry at the study site.

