9.2 SECONDARY ENDPOINTS

- 1) The frequency, percentage and 95% confidence interval of the changes from baseline to 12 and 24 weeks will be summarized for patients who had HbA1c reaching less than 7% (target effectiveness response rate).
- 2) The frequency, percentage and 95% confidence interval of the changes from baseline to 12 and 24 weeks will be summarized for patients whose HbA1c was decreased by at least 0.5% at the last visit (relative effectiveness response rate).
- 3) For FPG, Weight, SBP and DBP, the changes from baseline to 12 and 24 weeks will be summarized using number of subjects, mean, SD, median, minimum, maximum, 5th percentile and 95th percentile, and will be compared using paired t-test.
- 4) Mean difference in the change of HbA1c from baseline to latest value according to following variables will be analyzed using t-test or ANOVA (Analysis of Variance).
 - Age group (Less than 19 years, 19 years or older and less than 30 years, 30 years or older and less than 40 years, 40 years or older and less than 50 years, 50 years or older and less than 60 years, 60 years or older)
 - Gender (Male, Female)
 - Height (<median, \geq median)
 - Weight (<median, \geq median)
 - Smoking status (Never smoked, Ex-smoked, Currently smokes)
 - Duration of disease (<median, \geq median)
 - Family history of T2DM (Yes, No)
 - Previous allergy (Yes, No)
 - Diabetes mellitus complications (Retinopathy, Neuropathy, Nephropathy, Vasculopathy, Other) (Yes, No, Not applicable)
 - Medical history (Yes, No)

CONFIDENTIAL

STATISTICAL ANALYSIS PLAN

- Comorbidities (Yes, No)
- Prior medication (Yes, No)
- Concomitant medication (Yes, No)
- Other anti-diabetic agent (Yes, No)
- Geriatric population (65 years or more, Less than 65 years)
- Pregnant women (Yes, No, Not applicable)
- Renal impairment (Yes, No)
- Hepatic impairment (Yes, No)
- Long-term use (24 weeks or more)
- Total period of drug use (<median, \geq median)
- Total number of administration (<median, \geq median)
- Average number of administration per day (<median, \geq median)
- Reasons for early interruption (Change to other antidiabetics, Consent withdrawal, Adverse events, Patient refusal to continue taking study medication, Follow up loss, Others)

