9.4 UNIVARIATE ANALYSIS

The following categorical variables will be summarized using number of subjects, number of efficacy, efficacy rate and 95% confidence interval. Efficacy will be analyzed using Pearson's chi-square test or Fisher's exact test to determine if statistically significant differences exist. (However, if [Diabetes mellitus complications] responds with [Not applicable], [Pregnancy]

CONFIDENTIAL

STATISTICAL ANALYSIS PLAN

responds with [Not applicable], [Height] responds with [Not done], it is excluded from Pearson's chi-square test or Fisher's exact test.)

- Gender (Male, Female)
- Smoking status (Never smoked, Ex-smoked, Currently smokes)
- Family history of T2DM (Yes, No)
- Previous allergy (Yes, No)
- Diabetes mellitus complications (Retinopathy, Neuropathy, Nephropathy, Vasculopathy, Other) (Yes, No, Not applicable)
- Medical history (Yes, No)
- Comorbidities (Yes, No)
- Prior medication (Yes, No)
- Concomitant medication (Yes, No)
- Other anti-diabetic agent (Yes, No)

The following continuous variables will be summarized using number of subjects. Efficacy will be summarized using odds ratio and 95% confidence interval by using simple logistic regression.

- Age (years)
- Height (cm)
- Weight (kg)
- Duration of disease (years)
- Total period of drug use (days)
- Total number of administrations
- Average number of administration per day

Subjects of special investigation will be summarized using number of subjects, number of efficacy, efficacy rate and 95% confidence interval. Efficacy will be analyzed by using Pearson's chi-square test or Fisher's exact test to determine if statistically significant differences

CONFIDENTIAL

STATISTICAL ANALYSIS PLAN

exist.

- Geriatric population (65 years or more, Less than 65 years)
- Pregnant women (Yes, No, Not applicable)
- Renal impairment (Yes, No)
- Hepatic impairment (Yes, No)
- Long-term use (24 weeks or more)

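### HbA1c change is tested against height, weight and duration of disease only after a median split, which costs precision that a regression on the continuous value would keep

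*SAP*

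**What the plan says.** SAP 9.2 item 4 sets out the factor analysis of HbA1c: "Mean difference in the change of HbA1c from baseline to latest value according to following variables will be analyzed using t-test or ANOVA". Three baseline measurements enter as two-level factors: "Height (<median, \geq median"), "Weight (<median, \geq median") and "Duration of disease (<median, \geq median"). Age enters in fixed ten-year bands, with everyone aged 60 or over in one band. SAP 9.7 item 4 repeats the list for the long-term effectiveness set. The results go to tables D5 and D15.

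The exposure variables are coded in the same way, for example "Total period of drug use (<median, \geq median").

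SAP 9.4 lists age, height, weight and duration of disease as continuous, for instance "Duration of disease (years"), and says: "Efficacy will be summarized using odds ratio and 95% confidence interval by using simple logistic regression". SAP 8.3.1 does the same for the occurrence of adverse events.

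The method comes from protocol 9.7.3 item 2, under which differences in HbA1c change by "demographic parameters mentioned in 9.7.1 should be analyzed using t-test or ANOVA". The list in protocol 9.7.1 includes age, body weight and disease period. It names no cut points for body weight or disease period, and it does not list height. Neither document explains the median split.

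**The concern.** A median split treats two patients just either side of the cut as different and all patients on one side as alike. If HbA1c response changes gradually with weight or duration of disease, the two-group test sees only part of that gradient. SAP 5.2 applies a two-sided 5% level to these tests, so a non-significant split could be read as no relation when the analysis simply lacked precision.

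The cut is also defined by the sample. SAP Table 3 fixes the age bands and the cut at 65 years in advance, but gives no values for height, weight or duration. A result for patients at or above the median cannot be applied elsewhere until the median is known. If the median is recomputed in the long-term set, D5 and D15 may use different groups under one label.

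At stake is the precision and readability of a set of exploratory results, not a main conclusion of the study.

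**Working it through.** **Plan's own figure.** There is none to reproduce. The documents give no power, effect size or efficiency for the factor analyses, and SAP 2.2 bases the 600 patients on a regulatory requirement.

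**Inputs.** From the documents: 600 enrolled (SAP 2.2); two-sided 5% (SAP 5.2). Assumed: the shape of each factor, a linear effect, the correlation r between factor and HbA1c change, and the number analysed n. The effectiveness set will be no larger than 600, by an amount not stated.

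**Step 1: information kept by the split.** With a linear effect, the share kept is the squared correlation between the factor x and the indicator that x is at or above its median.

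- Standard normal x: correlation = E|x| = √(2/π) = 0.798; squared = 2/π = 0.637. Loss = 36%. 600 × 0.637 = 382.
- Uniform on (−1, 1): mean of |x| = 0.5, variance = 1/3, so the share kept is 0.25 ÷ (1/3) = 0.75. Loss = 25%.
- Exponential with mean 1: the means above and below the median are 1 + ln 2 and 1 − ln 2. Half the gap is 0.693 and the SD is 1, so the share kept is 0.693² = 0.480. Loss = 52%.

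Simulation with 1,000,000 draws confirmed these three and gave further shapes:

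| Assumed shape of factor | Information kept | Loss |
|---|---|---|
| Uniform | 0.750 | 25% |
| Height as an equal two-sex mixture (means 171 and 158 cm, SD 6, assumed) | 0.691 | 31% |
| Normal | 0.637 | 36% |
| Gamma, shape 3 | 0.580 | 42% |
| Gamma, shape 1.5 | 0.528 | 47% |
| Lognormal, sigma 0.5 | 0.517 | 48% |
| Exponential | 0.480 | 52% |
| Lognormal, sigma 0.8 | 0.371 | 63% |
| Lognormal, sigma 1.0 | 0.270 | 73% |

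**Step 2: effect on power.** Using Fisher's z, power ≈ Φ(atanh(r) × √(n − 3) − 1.96). For the split of a normal factor, r is replaced by 0.798r.

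With n = 550 and r = 0.12:

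- Continuous: atanh(0.12) = 0.1206; × √547 = 23.39 gives 2.820; minus 1.96 = 0.860; power 0.805.
- Split: 0.798 × 0.12 = 0.0957; atanh = 0.0960; × 23.39 = 2.246; minus 1.96 = 0.286; power 0.613.

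| Assumed n | Assumed r | Power, continuous | Power, median split |
|---|---|---|---|
| 600 | 0.12 | 0.84 | 0.65 |
| 600 | 0.10 | 0.69 | 0.50 |
| 550 | 0.12 | 0.81 | 0.61 |
| 550 | 0.10 | 0.65 | 0.46 |
| 400 | 0.12 | 0.67 | 0.48 |
| 400 | 0.10 | 0.52 | 0.36 |

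As a check on the formula, 6,000 simulated studies with n = 600 and r = 0.115 gave 0.80 and 0.61, against 0.81 and 0.61 from Fisher's z.

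**The case against.** The strongest defence is that the protocol itself prescribes a grouped comparison. A t-test or ANOVA on weight or duration cannot be run without groups, so the SAP had to choose a cut, and the median is a mechanical rule that nobody can tune. This stands. The SAP does not breach the protocol, and replacing the named test would itself be a departure. The signature record attached to the SAP is dated 19 April 2023, after the planned end of data collection on 30 November 2022, so new cut points chosen now could be chosen with data in hand. What the defence does not cover is why the grouped test should be the only analysis.

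It is also fair that the stakes are low. The abstract of the protocol calls all analyses descriptive, the primary objective is safety, and these are unadjusted factor tests in a single-arm study.

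Two stronger readings are tempting, and the documents do not support them:

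- A reader might infer that D5, D15 and the SAP 9.4 models could disagree about a factor purely because of coding. SAP 9.4 models a different outcome, the physician's rating of improved against unchanged or aggravated, and protocol 9.3.2.2.3 lets improved include maintenance. D15 also covers a different population, with at least 24 weeks of use and follow-up. Any of these could produce disagreement. The contrast shows that the continuous values are available and used, not that one analysis has two conflicting plans.
- A reader might infer that the medians will differ between the two sets. The SAP does not say whether they are recomputed, and because all patients are enrolled for 24 weeks the shift may be small.

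**Conclusion.** The point holds as a low-severity improvement. For height, weight and duration of disease, the only planned analysis of HbA1c change is a median split that the protocol does not ask for.

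The size depends on assumptions. A loss of about a third should not be read as a fact about this study: 36% applies to a roughly normal factor with a linear effect. It is smaller for a flatter distribution and could exceed half for duration of disease if that is strongly right-skewed. Under the normal assumption, the scenarios tabulated above lose about 0.16 to 0.20 in power. If the true relation is not linear, the comparison with a straight line changes.

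The paired HbA1c change in SAP 9.1 and the safety results are untouched.

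**What to change.** In SAP 9.2 item 4 and 9.7 item 4:

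- Keep the t-test/ANOVA table named in the protocol as a display.
- Add a linear regression of HbA1c change on each of age, height, weight and duration of disease as continuous variables. Report the slope per stated unit (for example per 10 kg or per 5 years) with its 95% CI, and make this the main result for those factors.
- Add a simple check of linearity for each, such as a smoothed plot or a quadratic term.
- If median groups stay in the display, use the effectiveness-set median in both D5 and D15 so that the groups match, and print its value.
- Record the addition in SAP 11, which at present lists only the change from average daily dose to average number of administrations.

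The three exposure variables share the coding but accrue during follow-up, so they are left out of this change.

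The cost is four short models per analysis set on data already collected, a linearity assumption that must be checked, and an addition to the protocol-named method that must be declared.

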8.3 SAFETY ANALYSES BY FACTORS

8.3.1 Univariate analysis

The following categorical variables will be summarized using number of subjects, the number of subjects and proportion of the number of subjects with AE and 95% confidence interval. AE Occurrence will be analyzed using Pearson's chi-square test or Fisher's exact test to determine if statistically significant differences exist. (However, if [Diabetes mellitus complications] responds with [Not applicable], [Pregnancy] responds with [Not applicable], [Height] responds with [Not done], it is excluded from Pearson's chi-square test or Fisher's exact test.)

- Gender (Male, Female)
- Smoking status (Never smoked, Ex-smoked, Currently smokes)
- Family history of T2DM (Yes, No)
- Previous allergy (Yes, No)
- Diabetes mellitus complications (Retinopathy, Neuropathy, Nephropathy, Vasculopathy, Other) (Yes, No, Not applicable)
- Medical history (Yes, No)
- Comorbidities (Yes, No)
- Prior medication (Yes, No)
- Concomitant medication (Yes, No)
- Other anti-diabetic agent (Yes, No)

For the following continuous variables AE Occurrence will be summarized using odds ratio and 95% confidence interval for an increase or decrease per defined unit of the variable based on using simple logistic regression.

- Age (years)
- Height (cm)
- Weight (kg)

CONFIDENTIAL

STATISTICAL ANALYSIS PLAN

- Duration of disease (years)
- Total period of drug use (days)
- Total number of administrations
- Average number of administration per day

Subjects of special investigation will be summarized using number of subjects, number of subjects with AE, proportion of subjects with AE and 95% confidence interval. AE Occurrence will be analyzed by using Pearson's chi-square test or Fisher's exact test to confirm statistically significant differences.

- Geriatric population (65 years or more, Less than 65 years)
- Pregnant women (Yes, No, Not applicable)
- Renal impairment (Yes, No)
- Hepatic impairment (Yes, No)
- Long term use (24 weeks or more)

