10.5 DETAILS OF SERIOUS UNEXPECTED AEs

The details of Serious Unexpected AEs collected from use result surveillance, special study (Pharmacoepidemiology study, etc.), clinical trials and Spontaneous reporting will be presented in a listing.

11. Changes to the planned analysis method

In the 9.7.1 demographic analysis item of Protocol (version 4.0), it is described that the administration status of this drug (average daily dose) is analyzed, but since Esglito is a composite, the average number of administrations per day will be analyzed.

[figure not shown]
12. SAS program code

The following SAS program codes will be used.

Table 6 SAS program code

Analysis method	SAS program code
Pearson's chi-square test or	PROC FREQ DATA=dataset;
Fisher's exact test	TABLE ae*factor/CHISQ EXACT; RUN;
Paired t-test	PROC UNIVARIATE DATA=dataset; VAR diff;

CONFIDENTIAL

STATISTICAL ANALYSIS PLAN

Analysis method	SAS program code
	RUN;
t-test	PROC TTEST DATA=dataset; CLASS factor; VAR chg; RUN;
ANOVA	PROC MIXED DATA=dataset; CLASS treatment; MODEL variable=treatment; LSMEANS treatment / PDIFF CL; RUN;
Simple logistic regression	PROC LOGISTIC DATA=dataset; CLASS factor; MODEL ae=factor; RUN;
Multiple logistic regression	PROC LOGISTIC DATA=dataset; CLASS factor1 factor2 factor3; MODEL ae= factor1 factor2 factor3 factor4; RUN;

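### The HbA1c-change test by pregnancy keeps *Not applicable* as a third group, although the SAP drops that answer from its other tests by pregnancy

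*SAP*

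**What the plan says.** SAP 9.2 item 4 sets the analysis: "Mean difference in the change of HbA1c from baseline to latest value according to following variables will be analyzed using t-test or ANOVA (Analysis of" (cut off inside the spelled-out name of ANOVA). The list beneath it has 23 entries. Three matter here:

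- "Pregnant women (Yes, No, Not applicable"
- "Gender (Male, Female"
- "Diabetes mellitus complications (Retinopathy, Neuropathy, Nephropathy, Vasculopathy, Other) (Yes, No, Not applicable"

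SAP 9.7 item 4 gives the same pregnancy, gender and complications entries for the long-term effectiveness set. Neither item says what happens to *Not applicable* in the test.

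The SAP does have a rule for that answer, in two other places. In 8.3.1 (adverse events), for pregnancy: "Pregnancy] responds with [Not applicable], [Height] responds with [Not done], it is excluded from Pearson's chi-square test or Fisher's exact test". In 9.4 (final effectiveness evaluation) the wording is the same: "responds with [Not applicable], [Height] responds with [Not done], it is excluded from Pearson's chi-square test or Fisher's exact test". In both places it also covers the complications answers, and in both it names only the chi-square and Fisher tests.

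The ANOVA program in SAP section 12, Table 6, is a one-way model on the class factor with no subsetting statement: "MODEL variable=treatment; LSMEANS treatment / PDIFF CL; RUN". SAP 5.2 (general considerations) and 6.1 (missing data) do not remove the level either. No passage defines *Not applicable* for pregnancy.

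**The concern.** A reader of Tables D5 and D15 will take the p-value in the pregnancy row as evidence on whether HbA1c change differs between pregnant and non-pregnant patients. With three levels, the F test asks whether the means of *Yes*, *No* and *Not applicable* are all equal. Its result can then be driven by a difference between the two groups that contain no pregnant patients.

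Pregnant women are a named special-investigation group (Protocol 9.2.2.4, SAP 4.6), so this row is likely to be read. One report would also treat one variable in two ways: *Not applicable* excluded in the final-effectiveness tables, included in the HbA1c tables.

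**Working it through.** The plan gives no power, effect size or SD for this analysis, so there is no figure of its own to reproduce. The check is how often the three-level F test rejects when pregnancy has no effect.

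**Inputs from the documents.** N = 600 (SAP 2.2); two-sided 5% level (SAP 5.2); three factor levels and a one-way model (SAP 9.2 item 4, Table 6).

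**Assumptions, not in the documents.** *Not applicable* means men; half the patients are men; 3 patients are pregnant; men and women differ by d in mean HbA1c change, in SD units, with d from 0 to 0.3; HbA1c change is normal with common SD; pregnancy effect zero.

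**Three groups (300 men, 297 *No*, 3 *Yes*).** The overall mean is 300d/600 = d/2, so every group mean lies d/2 from it. The noncentrality of the F test is

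λ = Σ nᵢ(μᵢ − μ̄)² / SD² = 600 × (d/2)² = 150d².

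The test has 2 and 597 degrees of freedom, with critical value 3.01.

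| d | λ | Rejection, noncentral F | Simulated (4,000 runs) |
|---|---|---|---|
| 0 | 0 | 5% | 4.9% |
| 0.1 | 1.5 | 17.8% | 17.6% |
| 0.2 | 6.0 | 58.2% | 58.3% |
| 0.3 | 13.5 | 91.7% | 92.1% |

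**No pregnant patients.** The factor reduces to *No* versus *Not applicable*, which under the assumption is the Gender test. With 300 per group, power = Φ(d/√(2/300) − 1.96). At d = 0.2 this is Φ(2.449 − 1.96) = 0.688. At 0.1 and 0.3 it is 0.231 and 0.957. Simulation gave 24%, 69% and 95%.

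**If *Not applicable* is not only men.** Code half the women that way too (448 *Not applicable*, 149 *No*, 3 *Yes*). The *Not applicable* mean becomes 300d/448 = 0.67d, and

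λ = 448 × (0.67d − 0.5d)² + 152 × (0.5d)² ≈ 51d² (with 0.67 unrounded).

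Simulated rejection falls to 8%, 23% and 44%. A separate run with 2 pregnant patients at d = 0.2 gave 57% with men only, and 37%, 23% and 13% with 25%, 50% and 75% of the women added.

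**Smaller analysed set.** With N = 480, half men and 2 pregnant patients, rejection is 14%, 50% and 85% at d = 0.1, 0.2 and 0.3.

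**The direct contrast.** In the 3-pregnant case the pairwise Yes versus No comparison printed by LSMEANS / PDIFF rejects in 5.0%, 5.0% and 4.9% of runs at the same three differences. If *Not applicable* is removed and *Yes* is compared with *No* by t-test (2 or 5 pregnant, N = 600 or 480, 40% to 60% men), rejection is 4.4% to 5.8% whatever the sex difference.

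**The case against.** The best counter-argument is that listing three levels does not show that three levels are tested. SAP 8.3.1 and 9.4 print the same pregnancy line and still drop *Not applicable* from the test. *Long-term use* appears in the same 9.2 list with a single level that could not be tested as printed. The exclusion also names Height, which is grouped into categories only in 9.2 and 9.7. That suggests the sponsor thinks of it as a rule about the variable and simply did not repeat it. The table shells, a separate document, might settle the matter.

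This makes an oversight likely. It does not make the text right: 8.3.1 and 9.4 needed an explicit sentence to drop the level, the sentence names two tests, and neither is used here. A programmer following 9.2 item 4 and Table 6 would keep the level.

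Other objections stand and limit the point:

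- A reader might infer that the ANOVA simply compares men with women. The documents do not define *Not applicable*, and the size of the effect depends heavily on what it contains.
- A reader might infer that a false pregnancy finding is to be expected. It needs a real difference between *No* and *Not applicable* patients, and the documents give no figure for one.
- The planned output partly exposes the problem. The Yes versus No contrast is printed when pregnant patients exist. In the simulated 3-pregnant case, when the pregnancy F test rejects, the Gender row also rejects in 83%, 97% and 99.5% of those runs at 0.1, 0.2 and 0.3 SD. With no pregnant patient, the empty *Yes* row would warn most readers.
- A reader might extend the charge of bias to the complications rows. They carry the same extra level, but nothing shows who would be coded *Not applicable* there or how that group would differ.

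**Conclusion.** The gap in the text is certain. SAP 9.2 item 4 and 9.7 item 4 do not carry over the exclusion used in 8.3.1 and 9.4, so the overall F test labelled pregnancy is not a test of pregnancy alone.

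The size of the harm is conditional. It ranges from none (5% rejection if the *No* and *Not applicable* groups do not differ) to about 92% at an assumed 0.3 SD sex difference with 3 pregnant patients and *Not applicable* meaning men, or about 95% with no pregnant patient. The error is confined to the overall F test or, when no patient is pregnant, to the *No* versus *Not applicable* comparison.

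Severity is minor. This is one of 23 listed factors in an exploratory secondary analysis, the protocol abstract describes the study's analyses as descriptive, and the primary safety objective is untouched. For the complications rows the case is consistency only; no bias has been shown there.

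**What to change.** Add one sentence to SAP 9.2 item 4 and the same to 9.7 item 4: *Not applicable* answers for pregnancy and for each diabetes complication are excluded from the t-test or ANOVA and shown as a descriptive row only, as in 8.3.1 and 9.4. Pregnancy is then compared *Yes* versus *No*. Add that the comparison is reported descriptively, without a test, when the *Yes* group is empty or too small to test, and state the minimum number. That last clause is new to the SAP. It also helps to state which patients the eCRF codes as *Not applicable* for pregnancy.

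The cost is a sentence or two in each of two sections and a subsetting condition in the program. No new data are needed. If Tables D5 and D15 have already been run, rerun these rows and record the change in the final report, as SAP section 1 requires.
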